13.3 SECONDARY ENDPOINTS Evaluation

To compare the rate of leukemia “positive” minimal residual disease (MRD) in the bone marrow at end of induction ($\geq 0.01\%$ mononuclear cells) in those who received the intervention as compared to historical controls.

The key secondary endpoint for efficacy is whether or not the bone marrow is “positive” for MRD at the end of induction (using the COG definition of $\geq 0.01\%$ mononuclear cells). From the retrospective study at CHLA of B-precursor ALL/obesity and end-induction MRD, 69 patients in the cohort had HR-ALL over the age of 10 at diagnosis. Of these, 53% of those overweight or obese (n=30) were MRD positive at the end of induction as compared to only 26% of those lean at diagnosis (n=39). Using this cohort as the historical comparison group, for the overweight/obese subset only, this study will have approximately 80% power to detect a reduction in the MRD positive rate to approximately that of the historical lean group (i.e from 53% to 24%) based on a two-sample, one-sided test of proportions with a Type I error of 0.10 (as a commonly used “go/no go” threshold to continue to Phase III trials). For the overall cohort, again in comparison to the historical cohort (MRD+ 38%, n=26/69) using a similar two-sample, one-sided test of proportions, the study will have the ability at $\sim 80\%$ power to detect a decrease in MRD by 20%. The study will therefore provide data on the potential reduction in the MRD positive rate that can be expected in preparation for the subsequent randomized Phase III trial for efficacy. These analyses will be adjusted for risk group, age, and other factors as appropriate and also compared to external published rates for MRD positivity.

To assess adherence to, and feasibility of, implementing a personalized and comprehensive dietary and exercise intervention during the first month of intensive chemotherapy

This endpoint will be reported as the proportion of study subjects who adhere to proposed dietary and activity interventions. A threshold of 80% of RD and PT visits (combined, RD only, PT only) completed will determine feasibility of incorporating the intervention itself into induction therapy. Adherence to each component of the intervention will be further assessed using a threshold of 75% MET-minutes prescribed/completed and 75% of dietary adherence prescribed/actual intake (overall, and to each macronutrient group). Further exploratory analysis will examine which sets of activities and dietary recommendations afforded the greatest level of adherence and any trends toward adherence by age, sex, race, and/or ethnicity.

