1.0 GOALS AND OBJECTIVES

1.1 Hypothesis:

In pre-adolescents, adolescents, and young adults (AYA) diagnosed with NCI/Rome High-Risk B-precursor acute lymphoblastic leukemia (HR-ALL), reducing gains in adiposity (i.e. fat mass) will improve leukemia sensitivity to induction chemotherapy, reduce post-induction minimal residual disease (MRD), reduce fatigue and obesity-associated toxicities, and improve quality of life.

1.2 Primary aim:

In AYA patients newly diagnosed with HR-ALL, to quantify the impact of a personalized dietary and activity intervention to mitigate chemotherapy-induced body fat gain throughout the critical first month of treatment ("induction").

1.3 Secondary aims:

In AYA subjects newly diagnosed with HR-ALL:

1. To compare the rate of leukemia "positive" minimal residual disease (MRD) in the bone marrow at end of induction ($\geq 0.01\%$ mononuclear cells) in those who received the intervention as compared to a historical controls.
2. To assess adherence to, and feasibility of, implementing a personalized and comprehensive dietary and exercise intervention during the first month of intensive chemotherapy

1.4. Exploratory aims:

In AYA subjects newly diagnosed with HR-ALL:

1. To evaluate persistence or extinguishing of this effect over months of continued dose-intensive pre-Maintenance phases of chemotherapy
2. To characterize the direct impact as compared to baseline of the intervention on self- and family- reported quality of life (QOL) outcomes including fatigue, mood, social interaction, and cognitive impairment reported via the PedsQL questionnaire and Child and Adolescent Scale of Participation (CASP) following the induction phase and serially during dose-intensive phases of chemotherapy.
3. To quantify the effect of adiposity on the activity of leukemogenic JAK2/STAT3, PIK3K/AKT/mTOR, MAPK/ERK, and other signaling pathways in leukemia cells as determined by kinase phosphorylation.
4. To quantify the effect of adiposity and of the intervention on the metabolic activity of leukemia blasts and of adipocytes as assessed by IGF-1, other obesity-associated cytokine signaling pathways, adiponectin, leptin, free fatty acid synthesis and metabolism, and levels oxidative stress.

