6.0 STUDY PLAN

6.1 SUMMARY OF STUDY PLAN

Pre-adolescent and AYA patients with newly diagnosed HR-ALL will have dietary and activity preferences assessed by a registered dietician (RD) and physical therapist (PT) at the start of induction.

Subjects will receive an individualized comprehensive dietary and physical activity plan. The RD and PT will devise a personalized dietary and activity intervention aimed at creating a minimum 10% caloric deficit each day (10% nutritional + exercise) throughout the four weeks of induction therapy. Adherence to the intervention will be assessed by the RD and PT at regular weekly intervals at routine clinic visits for chemotherapy and with home phone-calls between clinic visits. Home and hospital activity will also be recorded using a wearable electronic movement monitoring device (Fitbit ®) for all participants. A list of representative “menu” of possible activity interventions from which subjects may choose is provided as a separate Appendix. The primary efficacy of the intervention will be assessed in comparison to a recent historical control via determining the change in body fat percentage (and lean muscle) during induction as quantified by dual-energy x-ray absorptiometry (DXA). A key secondary aim will be the effectiveness of the intervention to reduce chemoresistance as evidenced by decreased prevalence of leukemia minimal residual disease (MRD) at the end of induction. MRD using multicolor flow cytometry is routinely assessed as a predictor of outcome in all patients with HR-ALL. Exploratory analyses will also examine biomarkers of the proposed mechanism including adiposity and intervention-related changes in leukemogenic signaling pathways, oxidative stress, and cellular metabolism. Parent- and subject-reported QOL assessments will consist of the PedsQL and Child and Adolescent Scale of Participation (CASP) surveys (see separate Appendix) and will be conducted pre- and post-induction and at two delayed time-points (mid-point of intensive chemotherapy [3 months from diagnosis] and at end of intensive chemotherapy phase [10 months from diagnosis] to assess the psychosocial benefits of the intervention.

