6.2 TREATMENT PLAN

6.2.1 DIETARY INTERVENTION

The dietary intervention will be performed by an RD and is designed to achieve an at minimum $\geq 10\%$ daily caloric deficit to prevent fat gain along with a moderate fat (20-25%), high protein (20-25%), and low glycemic index/high fiber carbohydrate (45-55%) nutritional plan to prevent loss of lean muscle mass loss and to maintain micronutrient intake. The subject’s basal metabolic rate (BMR) will be calculated using the Schofield equation as per the World Health Organization recommendations (World Health Organization, Energy and Protein Requirements, Technical Report Series 724, 1985) with an activity factor of 1.3 (“for a well-nourished child at bedrest with mild to moderate stress”) applied to better estimate the subject’s resting energy expenditure (REE) from which to calculate the initial 10% caloric deficit goal. At the initial counseling session, the dietitian and family will determine which dietary technique is most likely to lead to dietary adherence. Dietary management tools will incorporate the My Plate (USDA) and the Traffic Light Diet tools to help educate families regarding portion size and eating habits. The RD will use a menu of common foods that meet the intake goals above as well as help families choose “exchanges” on the menu to personalize the menu options to maximize adherence. During the initial

hospitalization, the RD will visit with the subject to assess caloric and nutrient intake using a 3-day food intake log, counsel subjects and their families on nutrition and eating habits, and instruct how to monitor food intake using a simplified log. If available, and if the family so desires, the option will be available for families to use their personal cell phone or digital camera to take pictures of meals (before consumption and after consumption) to email to the RD to help guide the dietary intervention.

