During subsequent weekly outpatient chemotherapy clinic visits (or if the subject remains hospitalized), the RD will follow-up with families on their perceived adherence and obtain intermittent dietary intake via 24 hour diet histories. Between clinic visits, the RD will also contact the family to provide reinforcement/motivation, answer questions, and obtain interval dietary history if necessary. Specific dietary recommendations for foods/drinks, meals, and snacks will be adjusted weekly in discussion with families to meet the daily caloric deficit and goal diet as described. The caloric goals may also be adjusted $\pm 5\%$ depending on insufficient/excessive weight or body composition changes. At the end of the acute intervention, the RD will discuss with the subject and family their dietary status and sustainable healthy eating behaviors.

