minutes). For patients who do not complete (or do not bring) the study log, adherence will be assessed by the PT at the time of visit via subject self-report of days meeting activity goals. The following scale will be used: 0% (<1day/week), 25% (1-2days/week), 50% (3-4days/week), 75% (5-6days/week), 100% (7days/week). Reported activity must meet 100% of that recommended for each qualifying day. The exercise program will be progressive by nature such that the Daily Goal is increased each week depending on adherence, ability, and clinical condition.

All subjects will be provided a wearable electronic activity monitor (Fitbit®) to assist in recording home activity levels in minutes of activity; the Fitbit® has the important secondary benefit of providing visual reinforcement for the subject of their progress toward their Daily Goal as set by the study team.

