7.2 MODIFICATION OF DIETARY INTERVENTION

Similarly, a subject may not be able to adhere to the nutrition intervention for reasons such as, nausea/emasis or the treatment team determining the subject cannot receive liquids or food by mouth (NPO). In such instances, the study team will continue to track all data at specified time-points and the registered dietitian will re-assess nutritional caloric goals. Moreover, for subjects at lower BMI percentiles, despite the anticipated body fat gain, should the BMI percentile decrease to <5th percentile, the subject will come off-therapy as per Section 12.1.

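### The 75% diet-adherence threshold is looser than the 10% deficit it is meant to score: a subject eating 100% of estimated REE counts as adherent on every intake-ratio reading

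*Combined protocol and SAP*

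**What the plan says.** All references are to the combined protocol and SAP.

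- **Aim.** Section 1.3 lists as a secondary aim: "To assess adherence to, and feasibility of, implementing a personalized and comprehensive dietary and exercise intervention during the first month of intensive chemotherapy".
- **Prescription.** Section 6.1 describes a plan "aimed at creating a minimum 10% caloric deficit each day (10% nutritional + exercise", so the diet carries 10% and exercise comes on top. Section 6.2.1 estimates REE as Schofield BMR with an activity factor of 1.3, "from which to calculate the initial 10% caloric deficit goal". It prescribes a "moderate fat (20-25%), high protein (20-25%), and low glycemic index/high fiber carbohydrate (45-55%) nutritional plan" and lets the caloric goal move by ±5%.
- **Measurement.** Under Section 6.2.1 the dietitian is to "obtain intermittent dietary intake via 24 hour diet histories". The Section 9.1 table schedules a 24-hour recall at every visit and a 3-day food log at diagnosis and at end of induction. If a subject cannot follow the diet, Section 7.2 says that "the registered dietitian will re-assess nutritional caloric goals".
- **Scoring.** Section 13.3 reports the proportion of subjects who adhere. Feasibility is decided by completion of 80% of dietitian and physical-therapist visits. Adherence to each component is then assessed at 75%: for exercise on MET-minutes prescribed/completed, and for diet on "75% of dietary adherence prescribed/actual intake (overall, and to each macronutrient group".

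Section 13.3 gives no direction for the diet ratio, no ceiling on intake and no requirement that the deficit itself be met. No other section defines dietary adherence.

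**The concern.** A tolerance of 25% on intake is wider than the 10% reduction that the diet asks for, so the score may not separate subjects who cut their intake from those who did not. The failure that matters most here is eating too much: Section 2.2 names the appetite-stimulating effect of induction steroids as a cause of the fat gain that the trial wants to prevent.

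What is at stake is interpretation. If the DXA result is null and diet adherence is reported as high, a reader could conclude that the diet was delivered and did not work, when little or no dietary deficit had been achieved. Section 13.3 presents the study as preparation for a randomized Phase III trial, so that distinction would matter for the next design.

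**Working it through.** The plan states no sample size, power or error rate for adherence, so there is no figure of its own to reproduce. The check is direct arithmetic on the stated rule.

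**Inputs.** Initial deficit 10% of REE (Sections 6.1 and 6.2.1), so the goal is g = 0.90 x REE. Goal adjustment ±5% (Section 6.2.1). Threshold 75% (Section 13.3).

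**Step 1: score a subject eating 1.00 x REE at the initial goal.**
- Prescribed/actual = 0.90/1.00 = 0.90, above 0.75: adherent.
- Actual/prescribed = 1.00/0.90 = 1.11, above 0.75: adherent.
- ±25% band = 0.75 x 0.90 to 1.25 x 0.90 = 0.675 to 1.125 x REE, which contains 1.00: adherent.

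**Step 2: repeat after the ±5% adjustment.** The text does not say whether it is additive or multiplicative, so both are shown.

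| Goal (x REE) | Prescribed/actual | Actual/prescribed | ±25% band (x REE) |
|---|---|---|---|
| 0.85 (additive) | 0.850 | 1.176 | 0.638-1.063 |
| 0.855 (multiplicative) | 0.855 | 1.170 | 0.641-1.069 |
| 0.945 (multiplicative) | 0.945 | 1.058 | 0.709-1.181 |
| 0.95 (additive) | 0.950 | 1.053 | 0.713-1.188 |

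The subject at 100% of REE is adherent in every cell.

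**Step 3: find where the result would change.** The band excludes 1.00 only if 1.25g < 1, a deficit above 20%. Prescribed/actual fails only if g < 0.75, a deficit above 25%. Actual/prescribed never fails at this intake. The 10% is a minimum, so an individual goal could be deeper, but the plan states none beyond 20%.

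**Step 4: choose the likeliest reading.** For MET-minutes, the parallel clause in the same sentence, only a floor makes sense: completed/prescribed of at least 75%. Applied to diet this is actual/prescribed of at least 75%, which means intake of at least 0.75 x 0.90 = 67.5% of REE with no upper limit. For the macronutrients, fat would then have no ceiling, and protein prescribed at 20% of energy would pass at 20 x 0.75 = 15%, below the prescribed range.

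**Step 5: apply the 75% to the deficit instead.** The intake limit is 1 - 0.75(1 - g). At g = 0.90 it is 0.925. A subject at 100% of REE has achieved 0% of the deficit and fails.

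**Step 6: see how well a yes/no cut would classify.** Assume a day-to-day SD of 20-30% of REE (not in the documents) and 3-4 recalls. The SE of a subject's mean is then 20/√4 = 10.0 to 30/√3 = 17.3 points.
- Truly at goal (90%), fails the 92.5% limit: 1 - Φ(2.5/SE) = 0.40 to 0.44.
- Truly at 100%, passes it: Φ(-7.5/SE) = 0.23 to 0.33.

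**The case against.** **The documents do not support the strongest reading.** Taking the slash as an ordered ratio, a reader might infer that intake up to 0.90/0.75 = 120% of REE is formally allowed, and that any low intake, for example from nausea, counts as adherence without limit. But the same ordered reading of the MET-minutes clause would score a subject who did almost no exercise as adherent. Section 13.4 also sets prescribed against actual intake as a plain comparison. The slash most likely means prescribed versus achieved. Under actual/prescribed or the band, intake below 67.5% of REE fails. The missing upper limit and the pass at 100% of REE remain.

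**Other meanings are possible.** The 75% could be the share of the deficit achieved, which removes the problem, or the share of days at goal, which could. The fallback activity scale in Section 6.2.2 is day-based: "Reported activity must meet 100% of that recommended for each qualifying day". Neither meaning is written for diet, and the clause names intake. If one was intended, Section 13.3 needs to say so.

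**The consequence is limited.** Feasibility rests on visits, the adherence proportion has no pass mark, and recorded intake allows the mean deficit to be calculated later. This stands and limits the severity. It does not make the planned proportion informative.

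**REE is an estimate.** BMR x 1.3 assumes bed rest, and holding intake at that level on steroids may reflect real restraint. That is fair, but it is still not the prescribed 10% reduction.

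**A wide tolerance suits a few noisy recalls.** This is partly right: Step 6 shows that a tight cut misclassifies in both directions. It argues for leading with a mean, not for a cut that cannot detect the failure of interest.

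**Conclusion.** The point holds as one of endpoint definition, of minor to moderate severity. On all three intake-ratio readings, and across the ±5% adjustment, a subject with no dietary deficit relative to estimated REE is counted as adherent. On the likeliest reading there is no upper limit on intake. The diet-adherence proportion therefore cannot show whether the prescribed dietary deficit was delivered.

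This rests on the 75% being applied to intake, as the clause says, and on goals no deeper than 20% below REE for the band or 25% for prescribed/actual. It concerns the dietary part only, since exercise could still create a total deficit. The arithmetic in Steps 1 to 5 needs no outside figure; only the misclassification rates depend on assumed SDs.

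A reader might infer that the trial's feasibility decision or efficacy conclusions are compromised. They are not: the 80% visit rule, the DXA comparison, the MRD comparison and their power do not use this threshold.

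**What to change.** Change Section 13.3 only.

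1. **Main measure.** Define percent dietary deficit as 100 x (1 - recorded intake/(BMR x 1.3)). Average it per subject over all intake records that fall within the intervention: the 24-hour recalls, and the end-induction 3-day food log where its days fall inside the period. Report the mean with its 95% CI.
2. **If a yes/no measure is kept.** Apply the 75% to the prescribed deficit, so that intake must be at or below 92.5% of REE at the initial goal, with the limit recalculated by the Step 5 formula when the goal changes. Keep a lower bound, for example 75% of goal (67.5% of REE initially), so that very low intake is not scored as success.
3. **Macronutrients.** Score fat, protein and carbohydrate each against its prescribed range in Section 6.2.1.
4. **Involuntary low intake.** Keep NPO, tube-fed, parenteral and toxicity-limited days in the mean, because interpreting the DXA result needs the deficit actually received. Add a sensitivity summary without days recorded as NPO, tube-fed or parenteral.

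**Cost.** Some text and one derived variable. The recalls and food log are already scheduled in the Section 9.1 table, and its notes already list NPO, tube feeding and parenteral nutrition under clinical history. The sensitivity summary needs those entries to be dated.

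**Downside.** The adherent proportion will be lower. On a few records the yes/no cut misclassifies in both directions, at the rates in Step 6: about 40-44% of subjects truly at goal fail and 23-33% of those at 100% of REE pass. Self-report bias remains, and a confidence interval does not address it. For these reasons the mean should lead and any proportion should be supportive.

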13.4 EXPLORATORY ENDPOINTS EVALUATION

To evaluate persistence or extinguishing of this effect during continued dose-intensive phases of chemotherapy

Reported continued adherence to activity and dietary recommendations will be evaluated by the RD and PT as per last prescribed or recommended from the intervention versus actual minutes/dietary intake at the delayed time-points of start of Interim Maintenance ($\sim +3$ months) and start of Maintenance ($\sim +10$ months). Activity and dietary intake patterns will also be compared to baseline at-diagnosis levels. Similar exploratory analysis will examine the effect of age, sex, race, and/or ethnicity.

To characterize the direct impact as compared to baseline of the intervention on self- and family- reported quality of life (QOL) outcomes including fatigue, mood, social interaction, and cognitive impairment reported via the PedsQL questionnaire and Child and Adolescent Scale of Participation (CASP) following the induction phase and serially during dose-intensive phases of chemotherapy

The PedsQL questionnaire returns a QOL score between 0-100 for each patient at each time-point. The CASP is scored as a percentage and then normalized to a 100 point score. Differences during therapy will be compared using a two-sided, paired t-test during induction (the intervention) and using repeated measures analysis for all four time-points.

To quantify the effect of adiposity at diagnosis on the activity of leukemogenic JAK2/STAT3, PIK3K/AKT/mTOR, MAPK/ERK, and other signaling pathways in leukemia cells as determined by kinase phosphorylation

Differences in levels of expression of the pathways will be analyzed according to body fat percentage (adiposity) using a two-sided, two-sample t-test for the different pathways as well visually for overall trends in related pathways.

To quantify the effect of adiposity and of the intervention on the metabolic activity of leukemia blasts and of adipocytes as assessed by IGF-1, other obesity-associated cytokine signaling pathways, adiponectin, leptin, free fatty acid synthesis and metabolism, and levels oxidative stress.

Exploratory analyses using similar t-tests will be performed to explore the effects of adiposity at diagnosis on adipokines, obesity-associated cytokines, oxidative stress, and measures of cellular metabolism. The effect of the intervention on oxidative stress and free fatty acid synthesis will be analyzed using paired t-tests for pre/post intervention and compared to samples from the historical cohort.

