3.0 PRELIMINARY DATA

Obesity is a common problem in our patients with ALL.

In our cohort of adolescents with HR-ALL at CHLA, 48% were overweight or obese at diagnosis. Further, from the time of diagnosis to the end of the induction phase, subjects had an ~25% increase in body fat over these first 28 days of chemotherapy alone (from $23.3 \pm 9.1\%$ at time of diagnosis to $33.7 \pm 9.8\%$ at end of induction, $p < 0.001$, Fig. 1). Even more striking, this gain in body fat percentage was present in the entire cohort regardless of starting body composition (Fig 1.). Body fat then increased even further, to a mean of $37.1 \pm 7.9\%$ by the end of Delayed Intensification, following approximately seven months of intensive chemotherapy ($p < 0.001$, not shown). Overall, this increase in body fat represents a gain of 5.2 ± 4.9 kg of adipose tissue over the entire study period. Given our findings that adipose tissue can directly impair chemotherapy efficacy on ALL (32,33), this gain in body fat during such the critical chemotherapy dose-intensive treatment period is very concerning.

[figure not shown]

Fig 1. Body fat percentage measured by DXA scan in 10-21 year old children at diagnosis and end of induction. *** $p < 0.001$

Obesity impacts ALL survival within the first month of treatment. Treatment for childhood ALL generally lasts for 2-3 years. The first month of treatment (induction) is intense including prolonged high doses of steroids, and weekly chemotherapy, and frequent physician visits. Response to induction therapy through clearance of leukemia from the bone marrow as measured by flow cytometry and reported as “minimal residual disease” (MRD) is generally accepted as one of the best predictors of long-term survival (34). Given the association observed between obesity at diagnosis and EFS (1), we examined whether weight status at diagnosis would increase the risk of residual leukemia at the end of induction as measured by MRD. To do this, we retrospectively evaluated the records of 198 children treated at CHLA for B-precursor ALL. We observed that MRD positivity (as defined per COG by MRD with multicolor flow cytometry $\geq 0.01\%$) was increased in children who were overweight or obese (Fig 2 above).

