6.2.4 INTEGRATION OF INTERVENTION INTO ALL THERAPY

While induction chemotherapy for pediatric ALL is a highly morbid and overwhelming time, the study team has significant experience working both with this specific population as well as other populations with high morbidity. While lifestyle changes in general are difficult to achieve, short-term changes are generally more successful and patients and families in general are more receptive to short-term achievable goals.

In this context, the 28 day intervention proposed here is purposefully designed to naturally integrate into the four week induction phase beginning with the start of systemic chemotherapy. This phase routinely includes an initial hospitalization followed by weekly clinic visits with the treating provider for delivery of chemotherapy and evaluation of toxicity. The study intervention and assessments are therefore formulated around this routine clinical schedule.

Subjects will be enrolled surrounding the time of initial diagnosis within 24 hours of starting systemic chemotherapy. Children are routinely hospitalized for a minimum of four days from the start of systemic chemotherapy. During this time, they will have their baseline DXA scan (within 96 hours from start of systemic chemotherapy), the initial PT and RD assessments, and start with the supervised activity intervention and diet intervention. Bedside nursing will be available to provide reinforcement during that time. Following anticipated discharge, the subjects will be assessed at each weekly clinic visit to have their diet and activity interventions monitored and adjusted as needed and also to receive

education/motivation from the psychosocial team. At the final clinic visit at the end of induction, subjects will receive the post-intervention assessments along with additional motivation/education. Subjects will then continue on chemotherapy per routine care with ~8-9 additional months of intensive chemotherapy; subjects will receive PT, RD, and QOL assessments midway at the start of “interim maintenance” and again at the final time-point at the start of the low-intensity maintenance phase. These follow-up visits will help gauge whether the effect of the intervention and education extinguished or persisted during the intervening post-intervention months.

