13.2 PRIMARY ENDPOINT EVALUATION

The primary endpoint for efficacy is a reduction in gain of body fat percent (per DXA) from diagnosis to the end of induction. From data on 36 patients from the historical cohort at CHLA with DXA scans pre and post induction, there was a significant average fat gain during induction therapy of 5.5 ± 3.3 percent (mean \pm s.d.), $p < 0.001$. Based on a two-sample (36 historical, 36 present study) two-sided t-test with 5% Type I error, there will be at least 90% power to detect a 2.5 percentage point reduction in change in body fat as a result of intervention (e.g. from gain of 5.5 to a gain of 3.0%). Hence, this study has sufficient power to detect subtle, achievable effects on body fat during induction, and will with certainty detect stabilization of or a decrease in body fat during induction.

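### Does the exploratory aim on persistence need a body-fat analysis rather than the diet and activity comparison in Section 13.4?

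*Combined protocol and SAP*

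**What the plan says.** Section 1.4, exploratory aim 1, reads: "To evaluate persistence or extinguishing of this effect over months of continued dose-intensive pre-Maintenance phases of chemotherapy". It names no outcome. The primary aim in Section 1.2 concerns a diet and activity programme "to mitigate chemotherapy-induced body fat gain throughout the critical first month of treatment", and Section 13.2 states: "The primary endpoint for efficacy is a reduction in gain of body fat percent (per DXA) from diagnosis to the end of induction".

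Section 13.4 repeats the undefined phrase in its heading for this aim. The paragraph beneath it says "Reported continued adherence to activity and dietary recommendations will be evaluated by the RD and PT". The comparison is between what was last prescribed or recommended and the actual minutes and dietary intake, at the start of Interim Maintenance (about 3 months) and the start of Maintenance (about 10 months). Activity and diet are also compared with levels at diagnosis, and age, sex, race and ethnicity are explored.

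Section 6.2.4 says that "subjects will receive PT, RD, and QOL assessments midway at the start of" interim maintenance, and again at the start of maintenance. It adds that these visits help "gauge whether the effect of the intervention and education extinguished or persisted during the intervening post-intervention months".

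The schedule in Section 9.1 places height and weight, triceps skinfold and waist-to-hip ratio at both late visits. DXA appears only at diagnosis and at the end of induction.

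**The concern.** In Section 1.0 the phrase *this effect* most naturally points back to body fat. The hypothesis concerns adiposity, and the primary aim and primary endpoint are gain in body fat. On that reading the paragraph in Section 13.4 does not answer its own aim, because it contains no body-size outcome. The only late body-size data that the trial collects would also go unused in the stated analyses.

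If behaviour is meant, the worry is different: continued adherence might be reported as though the benefit on body fat had lasted. The historical cohort shows why that would matter. After induction, "Body fat then increased even further, to a mean of" 37.1% by the end of Delayed Intensification (Section 3.0), so fat can continue to rise whatever happens to behaviour. Leaving the outcome open until the data are seen would also leave room for selective reporting.

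**Working it through.** No sample size, power or alpha figure is attached to this aim, so there is no stated figure to reproduce. The check sets the sections side by side.

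**1. Is the aim made operational?** Section 13.4 gives each element of a descriptive comparison:

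| Element | Section 13.4 | Data in the plan |
|---|---|---|
| Outcome | Actual activity minutes and dietary intake | 24-hour recall at both late visits; Fitbit worn until study end (Section 9.1) |
| Reference 1 | Last prescribed or recommended amount | Dietitian and therapist prescriptions during induction (Section 6.2) |
| Reference 2 | Levels at diagnosis | Food log and recall at diagnosis (Section 9.1); therapist's baseline activity assessment (Section 6.2.2) |
| Times | About 3 and 10 months | Start of Interim Maintenance; start of Maintenance |

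Section 6.2.4 agrees. It lists therapist, dietitian and quality-of-life assessments at these visits, names no body measure there, and speaks of the effect of the intervention together with education. Quality of life has its own aim and its own repeated-measures analysis. The analysis of aim 1 can therefore be run as written.

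**2. Could persistence of the body-fat effect be estimated?** The primary effect is on DXA body fat percent. Section 10.0 counts two scans per subject, and the Section 9.1 footnote puts the second between days 29 and 36. No late DXA value exists, so no rewording makes this quantity estimable.

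**3. Would the late body measures fill the gap?** They would describe change over time within a single-arm cohort. Persistence of an effect also needs to be judged against the course without the intervention:

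- Historical rise after induction, from the Section 3.0 means: 37.1 − 33.7 = 3.4 percentage points.
- Section 3.0 implies an induction gain of 33.7 − 23.3 = 10.4 points, while Section 13.2 gives 5.5. If the 5.5 is applied to the Section 3.0 baseline (an assumption), the end-of-induction mean is 23.3 + 5.5 = 28.8 and the later rise is 37.1 − 28.8 = 8.3 points.

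Either way, fat rose under usual care. A later rise here could be the usual course and not a lost effect. The documents report no late historical BMI, skinfold or waist-to-hip values. The historical late point is at about seven months, against about ten here.

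**4. Does the historical rise size the problem?** No. Section 13.2 claims "at least 90% power to detect a 2.5 percentage point reduction in change in body fat". That is a between-group difference, whereas the 3.4 or 8.3 points are a within-cohort rise. Both are in DXA units, which this trial does not record after induction, so a ratio of the two says nothing about what Section 13.4 leaves out.

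**5. How much is unassigned?** Three measures at two late visits make 3 × 2 = 6 measure-visits. Section 13 does not name these measures as outcomes at the earlier visits either, and it specifies no late analysis for the lipid panel or research laboratory tests drawn at the same late visits. The anthropometrics are not a special omission.

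**6. Who would be available?** Section 13.1 expects 80% of the initial cohort at the last time-point. If that cohort is the 36 evaluable subjects, 0.80 × 36 = 28.8, about 29. If it is the 43 to 45 predicted eligible, 0.80 × 43 = 34.4 and 0.80 × 45 = 36. Nothing here turns on which is meant.

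**The case for a change.** The best case for a change is that both readings survive a full reading of the protocol, that body fat is the more natural one in Section 1.0, and that the remedy is cheap. A definition, plus a table or simple model for each body measure, needs no new visit or scan, and fixing the outcome beforehand limits selective reporting.

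Some of this stands. The phrase is undefined in both places, Section 13.4 names no statistical test for this aim, and the late body measures have no stated use.

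The step to a needed change does not stand. Adding the body measures would still not show that an effect persisted or was lost, because there is no late DXA and no documented matching comparator. Either route ends in a rewording or a descriptive table, which analysts can supply without altering the plan. Nothing in the protocol says that late adherence will be presented as lasting benefit on body fat, so the feared misreading is a point about reporting. Prespecification also carries less weight for an exploratory aim than for a primary or secondary one.

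**Conclusion.** No change to the plan follows. This is a loose phrase in an exploratory aim, and Section 13.4 resolves it in practice as persistence of diet and activity behaviour, in line with Section 6.2.4. Run as written, the late comparison is a sound description of behaviour. An analyst would sensibly label it so and summarise the late weight, skinfold and waist-to-hip data descriptively, without claiming that a body-fat effect lasted or faded.

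The size is small: one exploratory aim and six measure-visits with no named analysis, with no effect on the body-fat, MRD or feasibility analyses. The conclusion assumes that the Section 13.4 paragraph is the intended content of aim 1, and that late historical body measures at matching time-points are not at hand. If such data were available, a comparison could be informative, but it would still concern proxies and not the DXA endpoint.
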